2.2.1 Subgroup of interest

The primary endpoint(s), selected secondary [REDACTED] endpoints and selected safety endpoints will be evaluated using the subgroups defined in Table 2-1 where appropriate. Subgroup analyses for the study endpoints are represented in Table 2.2. [REDACTED]

Table 2-1 Subgroups definitions

Subgroup variables	Categories	Label for outputs	Suffix for outputs*
Randomization weight strata	body weight stratum (kg:<25, 25-<50, \geq 50)	Weight strata	a
Randomization disease severity strata	Disease severity strata (moderate, severe)	Disease severity strata	b
Age group	(<12 years or \geq 12 years)	Age group	c
Body weight and dose group*	AIN457 75 mg and <25 kg, AIN457 75 mg and 25-< 50 kg, AIN457 150 mg and \geq 50 kg; AIN457 150 mg and 25-< 50 kg, AIN457 300 mg and \geq 50 kg	Body weight by dose group	d

*In the final (Week 224) analysis, subjects will be accounted in their actual dose group and weight category group to evaluate doses adjusted to the body weight. Per protocol, a subject will change into a higher or lower weight category and dose, when the subject's weight moves into a different weight category for two consecutive visits. If such a change happens, starting from the next efficacy assessment after the dose change, the subject will be accounted in the new dose group (75 mg, 150 mg, 300 mg) and weight category group.

Table 2-2 Subgroup endpoints

Endpoint/analysis	Randomization strata including weight and disease severity	Age	Weight and by dose group
[REDACTED]			
Adverse event	X	X	X
PK concentration data			X
Demography and background characteristics	X	X	

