## Treatment Period

The treatment period is defined as randomization to Week 208. In this period the endpoints are assessed and subjects are followed for long-term safety and efficacy. Subjects will be randomized using 1:1 ratio into either secukinumab low dose or secukinumab high dose. Randomization will be stratified by body weight (< 25kg, 25-< 50 kg,  $\geq$  50kg) and disease severity (either moderate (PASI score 12-<20 and IGA 3 or 4 or PASI score  $\geq$  20 and IGA 3) or severe (PASI score  $\geq$  20 and IGA of 4), collected at Randomization Visit. The study aims to recruit at least 60 subjects with moderate disease severity and approximately 20 subjects with severe disease severity. It will be targeted to have at least 5 subjects in the < 25kg weight, and at least 10 subjects in each of the other two weight groups. Subjects will receive the appropriate dose based on their body weight category. If a subject moves into a higher or lower weight group at two consecutive visits with weight measurements during the maintenance (from Week 12 onwards as assessed at 4 weekly visits or during extension treatment period (as assessed at scheduled site visits), the subject will receive dosing according to the new (higher or lower) weight group respectively. The dose will be adapted starting from the visit of the second consecutive weight change.

Adolescents (12-< 18 years) and children (6-< 12 years) can be included from the beginning of this study, since the DMC has approved already the enrollment of children (6-< 12 years) in study CAIN457A2310.

All subjects will visit the study site at Randomization (Day 1) and at Weeks 1, 2, 3, 4, 8, 12, 16 during which they will receive either high-dose or low-dose secukinumab treatment subcutaneously. Additionally, subjects will visit the site at Weeks 13, 14, 15 to provide blood samples for pharmacokinetics.

During the Treatment period subjects will receive treatment of the assigned secukinumab dose every 4 weeks. However during Weeks 16-52 site visits will be scheduled every 8 weeks and from Weeks 64-208 site visits will be scheduled every 12 or 16 weeks, to minimize the burden on the subject. Subjects will have the option to receive treatment between scheduled visits at home, following instructions provided to the subject (if  $\geq$ 12 years old), parent or caregiver.

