### **5.5.4 Instructions for prescribing and taking study treatment**

All study treatments will be administered subcutaneously throughout the study. All doses of study treatments at scheduled site visits will be administered at the study site after the study assessments for the visit have been completed. Prior to administration to the subject, the study treatment will be dispensed by the qualified site personnel appointed at the study site.

For home administrations the processes described earlier at [Section 5.5.2](#) must be followed.

The first study treatment administration will occur at the Randomization Visit (Day 1), after all study scheduled assessments have been performed (and inclusion/exclusion criteria confirmed) and only after the scheduled blood samples have been drawn. Similarly, at each other visit, all study assessments should be completed prior to the administration of study treatment.

Subjects will be administered study medication weekly for the first 4 weeks of the treatment period and then every 4 weeks until Week 204.

During the Follow-up period, no study medication will be administered.

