Adverse events will be summarized by presenting, for each treatment group (including any AIN457), the number and percentage of subjects having any AE, having an AE in each primary system organ class and having each individual AE (preferred term). The relative frequencies and 95% confidence intervals within each system organ class will be presented for adverse event and serious adverse event in a panel graph (for DMC only).

Summaries will also be presented for AEs by severity and for study treatment related AEs. If a particular AE 'severity' is missing, this variable will be listed as missing and treated as missing in summaries. If a subject reported more than one adverse event with the same preferred term, the adverse event with the greatest severity will be presented. If a subject reported more than one adverse event within the same primary system organ class, the subject will be counted only once with the greatest severity at the system organ class level, where applicable.

The crude incidence of treatment emergent AEs may be repeated and presented by age, disease severity strata and by body weight strata subgroups.

The exposure time-adjusted incidence rate of treatment emergent AEs, SAEs and important identified or potential risks (level 1) in entire treatment period will be summarized, where data permits. Data will be reported by SOC and PT and presented by age, disease severity strata and body weight strata. Crude rate will also be evaluated. Summary by body weight and dose group may be evaluated in addition to the above.

Adverse events will also be reported separately by standardized or customized MedDRA queries (SMQ or CMQ/NMQ). The MedDRA version used for reporting the study will be described in a footnote.

The most common adverse events reported ($\geq z\%$ in any group for each preferred term in the SOC-PT table or $\geq z\%$ in any group for each grouping term table) will be presented in descending frequency according to its incidence in total AIN457 group (combining both AIN457 treatment groups) starting from the most common event. Here threshold value z is set to 2 (%) but it may be updated following review of the dry run outputs.

Separate summaries will be provided for study treatment related adverse events, death, serious adverse event, other significant adverse events leading to discontinuation and adverse events leading to dose adjustment or interruption.

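### SAP 2.2.1 (2023) ties regrouping after a dose change to the next efficacy assessment, so the optional weight-by-dose adverse event table counts 4 to 16 weeks at the new dose under the old one

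*SAP*

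**What the plan says.** The 2023 SAP, section 2.2.1, defines a subgroup by body weight and dose with five cells. A footnote to Table 2-1 states the aim: "In the final (Week 224) analysis, subjects will be accounted in their actual dose group and weight category group". It then sets the timing: "starting from the next efficacy assessment after the dose change, the subject will be accounted in the new dose group". Table 2-2 lists the endpoints for each subgroup, and its adverse event row ("Adverse event X X X") includes the weight-and-dose column. PK concentrations are marked in the same column but have their own regrouping rule in SAP 2.9. SAP 2.8.1 leaves the adverse event table optional: "Summary by body weight and dose group may be evaluated in addition to the above".

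Protocol 3.1 (Treatment Period) fixes when the new dose begins: "The dose will be adapted starting from the visit of the second consecutive weight change". Protocol 5.5.4 fixes the order within a visit: "at each other visit, all study assessments should be completed prior to the administration of study treatment". Neither the exposure definition (SAP 2.4.1) nor the rate method (SAP 5.4.5) splits time at a dose change.

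**The concern.** The timing rule suits PASI and IGA. These are scored at the visit before the new dose is given, so the scores at the dose-change visit belong to the old dose and the first scores under the new dose come at the following visit.

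Adverse events carry their own onset dates. An event that starts the day after the first new dose occurs on the new dose and in the new weight category. Under the footnote as written it stays in the old cell until the next efficacy visit, and so does the person-time. That works against the footnote's stated aim of counting subjects by actual dose. At stake is whether the cells of the weight-by-dose adverse event table describe the doses in their labels.

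**Working it through.** **Inputs.** Scheduled visit days: SAP Table 2-3. Dosing every 4 weeks, last dose at Week 204: Protocol 5.5.4. Treatment-emergent window to last dose + 84 days: SAP 2.8.1. Dose by weight cell: Protocol Table 5-1. I assume that the dose changes at a scheduled site visit and that PASI and IGA are done at each visit in Table 2-3.

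**The plan's own intervals.** Protocol 3.1 says that "during Weeks 16-52 site visits will be scheduled every 8 weeks" and that visits are 12 or 16 weeks apart over Weeks 64–208. From the scheduled days, the gaps over Weeks 16–52 are 8, 8, 8, 8 and 4 weeks. The gap from Week 52 to Week 64 is 12 weeks, and all later gaps are 12 or 16 weeks. The stated intervals reproduce except for Week 48 to Week 52: (365 − 337)/7 = 4 weeks.

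**Lag.** Lag = (day of next visit − day of dose-change visit)/7. New-dose injections given before regrouping = lag/4.

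| Dose-change visit (week) | Lag (weeks) | New-dose injections under the old dose | Intervals |
|---|---|---|---|
| 48 | 4 | 1 | 1 |
| 16, 24, 32, 40 | 8 | 2 | 4 |
| 52, 64, 76, 104, 116, 128, 156, 168, 180 | 12 | 3 | 9 |
| 88, 140, 192 | 16 | 4 | 3 |

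This gives 17 intervals, of which 4 + 9 + 3 = 16 lie between 8 and 16 weeks. The mean is (1×4 + 4×8 + 9×12 + 3×16)/17 = 192/17 = 11.3 weeks. If a change at Week 12 is possible, its lag is also 4 weeks. An unscheduled efficacy assessment would shorten any lag.

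**Share of new-dose time in the wrong cell.** For a subject treated to Week 204, the treatment-emergent window ends at Week 204 + 12 = Week 216. Share = lag/(216 − week of change).

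- Week 16: 8/200 = 4%
- Week 104: 12/112 = 11%
- Week 156: 12/60 = 20%
- Week 192: 16/24 = 67%. Counted only to Week 208, it is 16/16, because the injections at Weeks 192, 196, 200 and 204 all precede the Week 208 assessment.

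**Size of the dose step.** Of the four upward moves in weight category, three double the dose: 75 to 150 mg in the low-dose arm at 50 kg, 75 to 150 mg in the high-dose arm at 25 kg, and 150 to 300 mg in the high-dose arm at 50 kg. The fourth, low-dose arm at 25 kg, leaves the dose at 75 mg and changes only the weight cell.

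**Carry-over.** The last old dose is normally 4 weeks before the first new one, so last old dose + 84 days reaches 12 − 4 = 8 weeks past the change. Lags of 12 and 16 weeks exceed that by 4 and 8 weeks, which applies to 9 + 3 = 12 of the 17 intervals.

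**The case against.** The strongest reply is that the timing sentence was written for efficacy alone. It names only an efficacy assessment, the preceding sentence sets the principle of actual dose group, and the separate PK rule shows that the footnote's timing need not govern every row of Table 2-2. That is a fair reading of intent. If it is right, however, the plan has no visible regrouping rule for adverse events in a subgroup it assigns to them, and the programmer would have to choose one after the data are seen. The same sentence is needed either way. Parts of section 2.2.1 and Table 2-2 are redacted, so a rule there cannot be excluded.

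A second reply is that some attribution to the old dose is reasonable, because the SAP's own safety window runs 84 days past a dose. This stands for lags of up to 8 weeks. It does not cover the longer ones, and the SAP does not offer that window as a way to allocate events between dose levels.

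A third reply is that little depends on the table. This largely stands. SAP 2.8 presents the main safety summaries by low, high and any dose, and these do not use the footnote. The weight-by-dose split is descriptive, with no test or decision attached.

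A reader might also link the footnote to a health-authority request. The documents do not support that. The weight-by-dose summaries were added in 2019 after authority discussions (SAP document history and section 4), but the footnote was added in September 2023 for the final analysis only, and the change log gives no such origin.

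**Conclusion.** The point holds within a narrow scope. As written, the footnote puts adverse events and person-time from the 4 to 16 weeks after a dose change into the wrong cell. The share is small for early changes and large for late ones. It affects only subjects whose dose or weight cell changes, and only the optional weight-by-dose adverse event summary of the final analysis.

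A reader might infer that the rule hides a dose relationship, since growing children would mostly move up and early events at the higher dose are charged to the lower. The documents do not establish this. In the 25 to under 50 kg cells, children moving to 50 kg or more leave time at 150 mg in the 75 mg cell and time at 300 mg in the 150 mg cell. Both cells are contaminated with time at twice the dose, so the contrast between them need not shrink. Across weight categories, dose is tied to weight by design. A reader might also infer from the Week 192 case that all new-dose time is lost. That is true only to Week 208; over the treatment-emergent window it is 67%.

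The number of switchers is not given, so the effect on any event rate cannot be computed. The conclusion rests on reading the footnote literally for adverse events, on scheduled visit timing, and on there being no adverse event rule in the redacted text.

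**What to change.** Amend the Table 2-1 footnote in four respects:

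- Limit the next-assessment rule to PASI and IGA.
- For adverse events in this subgroup, assign each event to the dose and weight group in effect at onset, counted from the date of the first administration at the new dose. For a weight-cell move that leaves the dose unchanged, name the date that applies.
- In exposure-adjusted rates for this subgroup, split person-time at that date.
- State how a subject who contributes to two cells enters the crude denominators.

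The cost is a few sentences and a programming change. Administration dates, including home doses, are already recorded in the Dosage Administration Record eCRF (Protocol 5.5.2 and 6.3). There are two small downsides. A subject may appear in more than one cell, and some events soon after a change may carry over from the old dose. A table footnote can say both.

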2.3 Patient disposition, demographics and other baseline characteristics

Summaries will be reported by the following treatment groups:

Treatment for analysis

- AIN457 low dose
- AIN457 high dose
- Total

The following common background and demographic variables will be analyzed:

Continuous variables:

- Age in years (derived from year of birth and informed consent data, assuming date is July 1st since only year of birth is reported on the case report form (CRF))
- Height
- Weight
- Body mass index (BMI)

Categorical variables:

- Age categories (<12 years, 12 years and older)
- Gender
- Race
- Ethnicity
- Weight categories (<25 kg, 25-<50 kg, \geq 50 kg)
- Disease severity (moderate or severe)

Psoriasis specific baseline characteristics and history of disease will be summarized as well: baseline PASI, baseline PASI (\leq 20, $>$ 20), baseline total body surface area (BSA), baseline IGA mod 2011 score (moderate, severe), severity of psoriasis (as defined at randomization), psoriatic arthritis (yes, no), time since diagnosis of psoriasis, time since diagnosis of psoriatic arthritis, previous exposure to biologic systemic psoriasis therapy, previous exposure to systemic psoriasis therapy, previous exposure to non-biologic systemic psoriasis therapy, previous failure to biologic systemic psoriasis therapy, previous failure to systemic psoriasis therapy, previous failure to non-biologic systemic psoriasis therapy (including phototherapy and photo-chemotherapy). Summaries above will be repeated and presented separately by age group and body weight by dose group.

Body Mass Index (BMI) will be calculated using the following formula:

$$\text{BMI} = (\text{body weight in kilograms}) / (\text{height in meters})^2$$

For BMI, height and body weight the last value prior to randomization is used. If there is no weight recorded prior to taking of study treatment, BMI will be missing.

Time since diagnosis of psoriasis (PsO) and time since diagnosis of psoriatic arthritis (PsA) will be calculated using the following formula:

$$\text{Time since diagnosis} = (\text{inform consent date} - \text{first diagnosis date} + 1) / 365.25$$

The first diagnosis date of PsO or PsA will be imputed according to the imputation rules in Section 4.1 of MAP

Unless otherwise specified, summary statistics will be presented for continuous variables for each treatment group and for all subjects (total) in the randomized set. The number and percentage of subjects in each category will be presented for categorical variables for each treatment group and all subjects (total) in the randomized set.

Any condition entered on the *relevant medical history / current medical conditions* eCRF will be coded using the MedDRA dictionary. They will be summarized by System Organ Class (SOC) and Preferred Term (PT) of the MedDRA dictionary.

Unless otherwise specified, analyses will be based on the randomized set.

2.3.1 Patient disposition

The number of subjects screened will be presented. In addition, the reasons for screen failure will be provided. The number and percentage of subjects in the randomized set who completed study periods (treatment period and treatment free follow period) and who discontinued the study prematurely (including the reason for discontinuation) will be presented for each treatment group and all subjects.

For each protocol deviation, the number and percentage of subjects for whom the deviation applies will be tabulated by randomized treatment groups on the FAS population. All substantial protocol deviations will be displayed in the outputs.

2.4 Treatments (study treatment, rescue medication, concomitant therapies, compliance)

2.4.1 Study treatment / compliance

The analysis of study treatment data will be based on the safety set.

The number of secukinumab injections will be summarized by treatment group by means of contingency tables.

The duration of exposure to study treatment will be summarized by treatment group. In addition, the number of subjects with exposure of at least certain time thresholds (any exposure, ≥ 1 week, ≥ 2 weeks, ≥ 3 weeks, ≥ 4 weeks, and thereafter every 4 weeks, so ≥ 8 weeks, ≥ 12 weeks, etc.) will be displayed.

Duration of exposure will be defined as the time from first dose of study medication to the last dose plus 84 days or last visit (including follow-up visits) whichever occurs earlier. i.e., for subjects who discontinued or have their last visit earlier than last dose plus 84 days, the end of study treatment exposure will be the date of the last study visit in the follow-up period or in the corresponding treatment period.

Duration of exposure (days) = min ('end of treatment period' date, last dose date +84) – first dose date +1

Duration of exposure (years) = duration of exposure (days) / 365.25

Duration of exposure (100 subject years) = duration of exposure (years) / 100

The analyses of duration of exposure described above will be reported for the treatment period up to Week 16 for the PEA, with the last category " ≥ 16 weeks". Summaries on the entire treatment will be provided at Week 24 IA and thereafter.

Also, subjects who changed dose due to change of weight group will be listed if required.

2.4.1.1 Visit window

Visit-windows will be applied to data summarized by visit. These will be based on study evaluation schedule and comprise a set of days around the nominal visit day. For any assessment, there are the protocol defined scheduled visits around which visit windows are created to cover the complete range of days within the study. The visit windows are shown in

Table 2-3. In this table, the days are counted since the first dose of study treatment (study days) for safety assessments, and the days are counted since the date of randomization for efficacy assessments. These visit windows apply to measurements taken at every visit. For assessments collected less often different visit windows will be applied as detailed below.

When visit windows are used, all visits will be re-aligned, i.e., they will be mapped into one of the visit windows. E.g., if the *Week 4* visit of a subject is delayed and occurs on Day 60 instead of on Day 29, it will be re-aligned to visit window *Week 12*. In the case of major deviations from the visit schedule, or due to unscheduled visits, several assessments of a subject may fall in a particular visit window (either scheduled or unscheduled). Statistical approaches to handle multiple assessments in a given visit window are specified below.

The analysis visit will be used for listing of visit and period for safety data. If a visit falls after the last visit window, it is not assigned an analysis visit and will be listed under label “After Week xxx”.

Table 2-3 Assessment windows for scheduled visits

Analysis Visit	Week	Scheduled Day	Visit Window
Baseline	BSL	1	-28 days to Day 1*
Week 1	1	8	Day 2-11
Week 2	2	15	Day 12-18
Week 3	3	22	Day 19-25
Week 4	4	29	Day 26-43
Week 8	8	57	Day 44-71
Week 12	12	85	Day 72-99
Week 16	16	113	Day 100-141
Week 24	24	169	Day 142-197
Week 32	32	225	Day 198-253
Week 40	40	281	Day 254-309
Week 48	48	337	Day 310-351
Week 52	52	365	Day 352-407
Week 64	64	449	Day 408-491
Week 76	76	533	Day 492-575
Week 88	88	617	Day 576-673
Week 104	104	729	Day 674-771
Week 116	116	813	Day 772-855
Week 128	128	897	Day 856-939
Week 140	140	981	Day 940-1037
Week 156	156	1093	Day 1038-1135
Week 168	168	1177	Day 1136-1219
Week 180	180	1261	Day 1220-1303
Week 192	192	1345	Day 1304-1401
Week 208 (EOT)	208	1457	Day 1402-1471

Week 212	212	1485	Day 1472-1499
Week 216	216	1513	Day 1500-1541
Week 224 (EOF)	224	1569	Day 1542-1597

* Baseline measurement before the first drug administration for safety assessments and before the randomization for efficacy assessments.

For parameters which are not collected at every visit (e.g. weight, laboratory, [REDACTED], visit windows defined in Table 2-3 will be combined. For example, if a parameter is measured at Week 12 and Week 24 only, Week 12 visit window will extend from Day 2 to Day 99 (combining Week 1 to Week 12 visit windows), Week 24 will extend from Day 100 to Day 197 (combining Week 16 to Week 24). If more than one assessment falls into the interval, the rules defined in Section 2.4.1.2 below are applied.

